1. Is there any prior relationship with the subjects and the PI? (one or both may be checked as applicable)	 No  Yes	If yes, explain. Patients may be current and/or previous patients of the investigator. [name] serves as the assistant professor to surgical residents.
---	--	--

2. If you as the PI are a clinician, will subjects be drawn exclusively from your own sample base?	 No  Yes	If no, explain how subjects will be identified.
3. If no to Q2, will the subject's physician be consulted, contacted, or notified?	 No  Yes	If no, explain.
4. Will recruitment materials be used (videos, ads, flyers, etc.)?	 No  Yes	If yes, what types, and when and how will they be used?
5. Will subjects be paid for participating in the study, including but not limited to compensation for time, travel, etc.?	 No  Yes	If yes, explain.
6. Describe how subjects will be initially contacted (i.e. recruitment materials, letter, office visit, etc.)? Subjects will be initially contacted by [name] at their preoperative visit.		

E. Benefits: Do not list monetary payments as a benefit.

1. Are there benefits to the subject? (What are the benefits, if any, to the subject by participating in the study?)	Explain. There are no direct benefits to research participants.
2. Are there benefits to society? (What potential benefits to future individuals may the study provide?)	Explain. Yes. Information gathered from the study may benefit future patients undergoing hernia surgery by determining which mesh is better for use during these procedures. The study will increase knowledge on the different types of hernia meshes and the length of time it takes residents to perform the procedure.

F. Costs to Subjects: Explain the financial liability to the study subject; distinguish study related costs vs. routine care costs.

1. Are there study related costs to subjects that are not paid by the study?	 No  Yes	Explain. Participants will be responsible for covering routine care costs associated with doctor visits and the surgery. However, there are no extra costs associated with this study.

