helps patients to say how good or bad their health state is. This scale uses a line with two different extremes. The extremes can vary in forms. Some VAS can ask the patient to range their pain level or current health status on a rating of either 0-10 (with 0 being no pain and 10 being the worst possible pain) or by choosing a picture of a happy or sad face.

Patients with bilateral inguinal hernias (an abnormal opening or defect that occurs on both sides of the groin), either found preoperatively or intra-operatively, will be treated as one hernia and will have the same mesh placed on both sides. Cases will be performed by one attending using his standard technique for laparoscopic inguinal hernia repair.

Data to be collected will include the patients' demographic information (age, sex, race), comorbidities (if present), smoking history, drinking history, medications, allergies and previous surgeries.

Operative data will include the following: type of anesthesia (all patients will undergo general), technique of laparoscopic access, type and side of hernia (direct or indirect), size of mesh used, type and number of tacks used to secure mesh, operative time, blood loss, urine output, and type and technique of closure.

Postoperative data will include: length of hospital stay, perioperative complications, recurrence rate, patient pain score and patient's postoperative quality of life. Further follow up data will include an assessment of the patient's recurrence rate, pain scale and quality of life during the patient's 1-2 weeks, 6 months, and 1 year follow-up. The patient will also be asked to rate their pain and/or comfort level by using the CCS and/or the VAS. During their 1-2 weeks visit, the patient will be informed of the 6 and 1 year follow-ups. For the six (6) month and one (1) year follow-up the patient will be contacted by telephone and/or be asked to return to the SEAHEC Physician's Office. The patient will not be charged for any of these services. Subjects will be tracked and identified with the use of the research record that will be set up in EPIC. Patients will be associated with the study and their surgery admission will be associated with the study for billing and coding compliance. In case the above system does not work, as a secondary system, patients will be tracked using an excel spreadsheet.

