Resident will be approached by [name] prior to the initiation of the study. [name] will give the residents the information sheet and will explain the study to the

	
residents. Additional time to review the information sheet will be provided if needed. [name] will address and answer all concerns and questions of the residents pertaining to the study. If the residents agree to participate in the study, the study coordinator will obtain verbal consent from the consenting residents. There will be no repercussions to any residents that objects to being in the study.
 
Resident level (PGY level), participation in the case (percentage of resident involvement to be determined by attending physician), time to perform the three critical portions of the case (laparoscopic access and takedown of peritoneum, placement of mesh, closure of peritoneum, and closure) will all be documented. This is routinely done by the surgical residents.
 
Following the case, the resident will be given a performance scale (NASA-TLX) to grade his/her performance in conducting the surgery. This is not routinely done but is done for some surgical cases. The NASA-TLX is a publicly available, multi-dimensional scale designed to obtain workload estimates from one or more operators while they are performing a task or immediately afterwards. It contains 6 scales that will ask the residents to rate their mental demand, physical demand, temporal demand, performance, effort and frustration on a scale of very low to very high. This will take the resident no more than three (3) minutes to complete. Once the resident has completed the scale, they will return the scale to [name]. [name] will then give the scales to the study coordinator who will keep all the scales in a locked and secure place at SEAHEC. The scale will be linked to the study patient by entering the study patient's study ID number on the scale. The residents do not routinely complete the NASA-TLX for all surgeries but for some they do. The requirement for the completion of the NASA-TLX by the surgical residents will be new and specific for this study.
 
Descriptive statistics will be performed and outcomes and resident performance will be compared based on resident level and type of mesh used. A p-value of <0.05 will be considered significant.

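### Residents return their NASA-TLX self-ratings through a person who is very likely the surgeon who teaches them, which leaves a secondary-goal measure open to social-desirability bias; the scale is also labelled as performance when it measures workload.

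*Combined protocol and SAP*

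**What the plan says.** Part IV, item 2 says that after each operation "the resident will be given a performance scale (NASA-TLX) to grade his/her performance in conducting the surgery". It then describes the same instrument as "designed to obtain workload estimates from one or more operators". The six scales cover mental, physical and temporal demand, performance, effort and frustration, all described as running from very low to very high. The study patient's ID is written on the form.

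On collection: "Once the resident has completed the scale, they will return the scale to" a masked person, who "will then give the scales to the study coordinator who will keep all the scales in a locked and secure place at SEAHEC".

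Three other statements bear on who that person is:

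- Part II.D, item 1, on prior relationships between the investigator and subjects, says that a masked person "serves as the assistant professor to surgical residents".
- Part II.D, item 2 asks "will subjects be drawn exclusively from your own sample base", and the box for yes is checked.
- Part IV, item 2 states: "Cases will be performed by one attending using his standard technique for laparoscopic inguinal hernia repair".

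Part IV, item 1 makes residents' ease of use and time a secondary goal. Part IV, item 2 describes the study as open label. It ends by saying that outcomes and resident performance will be compared by resident level and by mesh, with p<0.05 taken as significant.

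**The concern.** Trainees are asked to rate how well they did, how hard they worked and how frustrated they were, and then to hand a case-identifiable form to someone who probably supervises them. Under those conditions respondents have a reason to shade answers towards what looks competent. Because the rating itself is altered at collection, no later analysis can undo it.

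Among the measures listed, the NASA-TLX is the only resident self-report bearing on ease of use. If its scores are pushed towards the favourable end, a real difference between meshes may be missed. If the push varies with training level, a difference between levels may be created or hidden.

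A second, separate problem is the label. If a workload score is reported as resident performance, the conclusion describes something the instrument was not built to measure.

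**Working it through.** The plan gives no effect size, standard deviation, power or sample-size figure for the NASA-TLX, so there is no number to reproduce. The check traces the form and then asks what each comparison would absorb.

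**Step 1: who handles the form first.** The recipient passes the forms on to the coordinator, so the recipient is not the coordinator. The investigator is a teacher of the residents (Part II.D, item 1), all patients come from the investigator's own practice (Part II.D, item 2), and one attending does every case (Part IV, item 2). Together these make the investigator, acting as the attending, the most likely recipient. The name is masked, so this remains an inference.

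**Step 2: whether the form is anonymous to that person.** It is not. The study ID leads to the case, and the attending would know which resident took part.

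**Step 3: whether a safeguard applies at that moment.** Three provisions come close, and none covers it:

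- The promise of no repercussions (Part IV, item 2) protects residents who object to taking part. It says nothing about the ratings of those who do.
- Coded sheets and databases without resident identifiers (Part II.C, item 2) govern the data after collection.
- Locked storage begins when the coordinator has the form, after the recipient has held it.

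No sealed return is described, and nothing says that the attending will not see individual ratings.

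**Step 4: what each comparison absorbs.** Write a reported rating as the true rating plus a bias *b*, which may depend on mesh and on resident level.

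- *By level:* observed difference = true difference + [*b*(level 1) − *b*(level 2)]. Residents are not randomised to a level, and nothing in the design makes the two bias terms equal. A wish to look competent could plausibly vary with training year, although the documents do not show that it does.
- *By mesh:* observed difference = true difference + [*b*(mesh A) − *b*(mesh B)]. Patients are randomised, so resident levels should be balanced between arms on average, and a bias that does not depend on mesh cancels. What remains is compression: if ratings crowd towards the favourable end, there is less room for a real difference to show. The bracket differs from zero only if residents shade differently by mesh. That is possible because they know which mesh was used, but the plan states no preference by the attending.

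**Step 5: the label.** Side by side, one sentence says the resident uses the scale "to grade his/her performance in conducting the surgery" and another says it is "designed to obtain workload estimates from one or more operators". Performance is one of six items. The analysis sentence then refers to resident performance without naming the measure, so a reader cannot tell whether it means the NASA-TLX, the timed portions of the case, or both.

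**The case against.** The strongest reply has four parts.

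1. *The recipient is not named.* This stands. A reader might infer that the documents establish hand-over to the operating surgeon. They establish only hand-over to someone other than the coordinator, with strong circumstantial support for the investigator. The sponsor can settle it at once.

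2. *A false mesh difference is speculative.* This stands as well. It is tempting to assume a mesh-linked shift and convert it into a false-positive rate. The documents do not support that. Part IV, item 1 says both meshes are used interchangeably with good results, the plan does not say that every case will yield a resident form, and nothing shows that the return route would cause such a shift. Residents know the mesh whoever collects the form, so a change of route cannot remove their own expectations about it.

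3. *The direction of the performance item is unknown.* A reader might conclude from the very-low-to-very-high description that the item runs opposite to the demand items and must be reversed. The form is not in the documents, and the plan mentions no total score. If the printed anchors already align the item with the others, reversal would introduce an error.

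4. *The timed portions could serve as the performance measure instead.* The documents do not make that case. Times are already collected and already part of the secondary goal. The wording suggests that residents may document them too, and treating speed as performance is a separate judgement.

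What survives is the absence of any protection of the ratings before the coordinator holds them, and the contradiction over what the scale measures.

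**Conclusion.** The point holds as a modest, inexpensive correction. The collection rule leaves self-ratings of performance, effort and frustration open to social-desirability bias. The comparison by resident level is the most exposed. For the mesh comparison the likely cost is sensitivity, with directional bias possible but not shown.

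The size of the bias is unknown and cannot be derived from the documents. The conclusion assumes that the masked recipient is the investigator, or another person with authority over the residents. If the sponsor shows otherwise, the routing concern largely falls away, while the labelling contradiction remains.

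A reader might go further and infer that the trial's main findings are at risk. They are not on this account: length of stay, complications, recurrence, pain and patient quality of life do not pass through this form. Only the secondary goal is affected.

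**What to change.** In Part IV, item 2:

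- Confirm the role of the person who now receives the completed form.
- Have the resident return it in a sealed envelope, or directly to the study coordinator. The study ID can stay on the form.
- State, there and in the residents' information sheet, that the attending will not see individual ratings.
- Describe and report the NASA-TLX as perceived workload, not as resident performance, and say in the analysis sentence which measure each comparison uses.
- Score the performance item according to the anchors printed on the form, and write that direction down before analysis.

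The cost is a few sentences and some envelopes, since the coordinator already stores the forms. The small downside is that the coordinator must chase missing forms. Blinding, patient procedures and the other data collected are unchanged.

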	
One main part of the procedure to repair a hernia involves the placement of a prosthetic (a device that substitutes for missing parts or pieces) mesh to reinforce the abdominal wall and allow for a tension free repair. The use of the mesh also helps to lower the recurrence rate (the chance that the hernia will come back). The most common type of mesh prosthesis that is placed in laparoscopic inguinal hernias is a polypropylene (the substance the mesh is composed of) mesh which has been shown to be safe and effective.
 
There is some emerging evidence that a "lighter weight" form of this mesh may improve quality of life outcomes following surgery and is the mesh currently being used at New Hanover Regional Medical Center for laparoscopic inguinal hernia repair. However, there are many different "light weight" polypropylene meshes on the market that are FDA approved and available for use. Currently, there are two different forms of the mesh being used interchangeably for the procedure at NHRMC. Both of these meshes have had good clinical outcomes.
 
The purpose of this research study is to evaluate the clinical effectiveness of the two meshes currently being used. The study may provide evidence on whether one mesh is more effective than the other. A secondary goal of the study is to evaluate the ease of use and time it takes residents to place and perform the surgery using these two different meshes. This information may make it possible to determine if one mesh is easier for residents to use during surgery and therefore take them less time to perform the procedure.
 
The effectiveness of the meshes will be measured by the patient's length of hospital stay, perioperative complications, recurrence rate, patient pain score and/or comfort level and the patient's postoperative quality of life.

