
2. Description of study design, methods, and procedures, describe the study in sequential order as it is to be conducted at this institution. The following should be included:
 
 ➤ type of experimental design ➤ study procedures: a sequential description of what will be asked of/done to subjects (to include identification and recruitment of subjects, consent process, treatment or intervention if applicable, length of participation, additional visits, follow-up, etc.) ➤ description and assignments of subjects to various arms of the study (if applicable) 	
This will be a prospective open-label randomized study conducted by [name] from the study's approval date to until December 31, 2015. Approximately five-hundred (500) subjects will be enrolled in this study.
 
Patients presented to NHRMC, the Outpatient Surgery Clinic, SEAHEC Physicians' Office, Inpatient Surgical Units at NHRMC and/or the Emergency Department for abdominal wall hernia repair during their pre-operative visit and who meet the inclusion and exclusion criteria will be counseled by [name] on surgical options for repair to determine if they would

- doses, frequency, and route of administration of medication and other treatment
- data that will be collected
- primary outcome measurements
- follow-up procedures
- If the study involves clinical activities, distinguish routine care procedures from those that are study specific

rather undergo an open or laparoscopic repair. If the patient is a candidate and agrees with undergoing the laparoscopic repair, they will be asked if they would like to participate in a randomized trial comparing two different meshes. If the patient agrees, he/she will be presented with information regarding this study. The study will then be explained to the patient by [name].

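### No primary outcome or visit is named for the mesh comparison, so five unranked outcomes each tested at 0.05 give about an 18–23% chance of at least one nominally significant result if the meshes are equal (correlation assumed 0–0.5)

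*Combined protocol and SAP*

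**What the plan says.** Part IV, item 1 (Purpose and rationale) sets the aim: "The study may provide evidence on whether one mesh is more effective than the other". It measures effectiveness by "length of hospital stay, perioperative complications, recurrence rate, patient pain score and/or comfort level and the patient's postoperative quality of life". None of these five is placed above the others. The same item does rank goals: "A secondary goal of the study is to evaluate the ease of use and time it takes residents". That puts the resident measures below the mesh question, but it does not order the patient outcomes.

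Part IV, item 2 schedules "recurrence rate, pain scale and quality of life during the patient's 1-2 weeks, 6 months, and 1 year follow-up". No visit is marked as the main one. Patients are to "rate their pain and/or comfort level by using the CCS and/or the VAS", so the scale is open too. No separate quality-of-life instrument is named, and the VAS is described as a rating of health state as well as of pain.

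The inferential plan is the last paragraph of item 2: descriptive statistics, then "outcomes and resident performance will be compared based on resident level and type of mesh used", and "A p-value of <0.05 will be considered significant". The prompt for item 2 asks for "primary outcome measurements"; the answer does not identify any.

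**The concern.** A single 0.05 threshold controls false positives at 5% for one test. Here it applies to every mesh comparison in an unranked list. If the two meshes perform identically, the chance that something in the list crosses 0.05 is well over 5%.

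The number of tests is not fixed either. It depends on whether each visit is tested, whether the CCS and VAS are both analysed, and whether pain and quality of life are one measure or two. Nothing in the available text stops those choices from being made once the data by mesh are known. A reader of the results could not tell a planned main finding from the most favourable of several. The study is randomised, enrols about 500 patients and is meant to inform the choice between two meshes in routine use, so that distinction matters.

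**Working it through.** **The plan's own figures.** The only design figures are the 0.05 threshold and the enrolment of about 500. The plan states no familywise error rate, power, effect size, standard deviation or event rate, so there is no error figure to reproduce.

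**Inputs from the documents**
- Threshold per test: 0.05 (Part IV, item 2).
- Effectiveness outcomes: 5 (Part IV, item 1).
- Follow-up visits: 3, for recurrence, pain and quality of life (Part IV, item 2).

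**Assumptions**
- Tests are two-sided (the plan does not say).
- Each test has its nominal 5% size, except where stated below.
- The test statistics are normal with a common correlation ρ of 0, 0.3 or 0.5. The documents give no correlations.

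**Formula.** With k tests and no true difference:
- ρ = 0: P(at least one p<0.05) = 1 − (1 − 0.05)^k.
- ρ > 0: P = 1 − ∫ φ(u) [Φ((c − √ρ·u)/√(1−ρ)) − Φ((−c − √ρ·u)/√(1−ρ))]^k du, with c = 1.96, integrated numerically.

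**One test per outcome.** For k = 5 and ρ = 0: 1 − 0.95^5 = 1 − 0.774 = 0.226. The integral gives 0.209 at ρ = 0.3 and 0.183 at ρ = 0.5. A simulation of 2 million draws at ρ = 0.5 also gives 0.183.

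**Other readings of the plan**

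| Reading | Count | k | ρ=0 | ρ=0.3 | ρ=0.5 |
|---|---|---|---|---|---|
| Pain and quality of life share an instrument | 5 − 1 | 4 | 18.5% | 17.4% | 15.6% |
| Five outcomes, once each | 5 | 5 | 22.6% | 20.9% | 18.3% |
| Every visit, shared instrument | 1+1+3+3 | 8 | 33.7% | 30.0% | 25.0% |
| Every visit, separate measures | 1+1+3+3+3 | 11 | 43.1% | 37.5% | 30.4% |
| As above, CCS and VAS both analysed | 11+3 | 14 | 51.2% | 43.8% | 34.8% |

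In the counts, the 1s are length of stay and complications. Each 3 is one measure at three visits.

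**Sensitivity of the five-test figure**
- Unequal correlations (pain with quality of life 0.3–0.5, all other pairs 0.1; 1,000,000 draws): 21.9–22.2%. If the recurrence test never rejects because events are rare: 17.8–18.2%.
- Higher common correlation: 14.8% at ρ = 0.7 and 10.2% at ρ = 0.9.
- Conservative exact tests: with 250 per arm (equal split assumed) and an assumed 2% event rate, Fisher's test has a true size of about 2.1%. Using 2% for both binary outcomes, ρ = 0 gives 1 − 0.95^3 × 0.98^2 = 17.7%; ρ = 0.3 gives 16.4% and ρ = 0.5 gives 14.6%.
- The same with pain and quality of life merged: 1 − 0.95^2 × 0.98^2 = 13.3% at ρ = 0, then 12.6% and 11.5%.

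**After the change.** One pre-named primary test at 0.05 has a 5% error rate. If all five outcomes were instead kept on an equal footing with Bonferroni (0.01 each), the rate would be 1 − 0.99^5 = 4.9% at ρ = 0.

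**The case against.** Four points can be made for the plan.

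1. **Source.** The introductory note to Part IV asks for a summary and not for text pasted from a protocol, so a fuller protocol may exist, and some pages were not available. This limits the finding to the available text. It does not remove the gap, because the form explicitly asks for primary outcomes and the answer gives none.

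2. **Modest language.** The analysis paragraph opens with descriptive statistics, the purpose is worded cautiously, and no rule says that one significant result makes a mesh the better one. This stands: the percentages are chances of a nominally significant comparison, not of declaring a better mesh. But a significance threshold is set and outcomes are compared by mesh, so the plan is still inferential.

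3. **18% is not a floor.** Merged measures, rare events tested exactly, or correlation above 0.5 each bring the figure below 18%, to about 11–15% in the lower cases. This also stands. Every such case calculated here remains at least twice 5%, and a very high common correlation is hard to expect among outcomes as different as stay, complications and recurrence.

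4. **The 8-, 11- and 14-test figures are upper-end.** Repeated visits and paired scales in the same patients would not be uncorrelated, and the plan does not say that every visit will be tested. At ρ = 0.7 the 14-test figure falls to 24.9%. These rows show what the plan leaves open and should not be quoted as the size of the problem.

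**Conclusion.** The concern holds. The available text names no primary mesh outcome, no primary visit and no multiplicity rule, and it leaves the pain/comfort scale open. With one two-sided test per outcome at nominal size, the chance of at least one nominally significant mesh comparison under no difference is 18–23% for a common correlation between 0.5 and 0. The exact value depends on correlations, event rates, choice of test and number of tests, none of which the documents supply. The figures are illustrations and not limits; the conclusion that the rate is well above 5% survives the less favourable assumptions tried. The planned looks at 100 and 250 subjects are described as safety reviews and are not counted. This is a worthwhile, inexpensive improvement and not a fatal defect.

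**What to change.** Before any analysis by mesh, and so before the first interim look if it shows data by mesh, write down one primary mesh comparison: one outcome, one instrument, one time point, by assigned mesh, at two-sided 0.05. The CCS at 1 year is one example; the choice belongs to the investigator. If a scale is chosen, collect it from every patient at that visit, whether by telephone or in clinic, so that the instrument is not left open.

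Declare the other mesh outcomes and visits secondary. Either adjust them by Holm's method or report them as estimates with 95% confidence intervals and no significance claim. Keep the resident measures as the separate secondary goal they already are.

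The cost is protocol and SAP wording, plus consistent use of one planned instrument at the primary visit. Secondary outcomes face a stricter threshold or lose their significance claims. Power for the chosen primary with about 500 patients cannot be worked out from the documents, because they give no standard deviation or effect size; the investigator would have to check it.
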